11.4 Pre-Exposure Prophylaxis (PrEP) Monitoring Plan

A non-ignorable level of PrEP use in the study population may impact the power of the study to assess vaccine efficacy by lowering the background HIV incidence. Although oral FTC/TDF as PrEP is currently not widely used in the HVTN 702 study population, prevalence of PrEP will be collected and monitored as a precaution. Specifically, measures of PrEP use will be reported by treatment arm to the DSMB, alongside other measures of study under-performance for assessing operational futility. In addition, both the study oversight group and the protocol team leadership will see treatment-arm-pooled estimates of PrEP use.

Dried blood spot (DBS) samples will be used to assess FTC/TDF use via an intracellular tenofovir diphosphate (TFV-DP) assay. Prevalence of FTC/TDF will be reported both as any detectable use and inferred effective use. Estimated percentages of person-years at-risk during any detectable FTC/TDF use and during inferred effective FTC/TDF use will be reported. The definition of effective use differs for men and women. Current knowledge about PrEP in MSM indicates consistent use of at least 4 doses a week is required to achieve substantial levels of protection. The lower quartile of simulated TFV-DP levels in DBS at 4 doses per week is 719 fmol/punch (Castillo-Mancilla et al., 2013). In iPrEx OLE, the protective levels of TFV-DP in DBS were quantified as 700 fmol/punch (Grant et al., 2014), that is, there were no infections at visits where TFV-DP concentration was 700 fmol/punch or greater. Current knowledge about PrEP in women indicates consistent use of 6-7 doses a week is required to achieve protection. The lower quartile of simulated TFV-DP levels in DBS at 6 doses per week is 1064 fmol/punch (Castillo-Mancilla et al., 2013). Therefore, we will define effective PrEP use as 700 fmol/punch or more for men, and 1,000 fmol/punch or more for women. Ongoing work with calibration of DBS from directly observed dosing studies may refine these thresholds.

11.4.1 DBS sampling plan

The proposed PrEP monitoring plan of collecting DBS samples on 1 day each month to estimate FTC/TDF prevalence is evaluated using simulations where DBS samples are only collected on certain days of each calendar month. Specifically, we compare plans that collect samples on 1 day each month, 2 days each month, or 3 days each month.

[figure not shown]
The following are assumed in the simulations: 1) DBS samples are only collected on specific

days of each calendar month (we compare plans to assay samples collected on the 10th, 15th, and 20th day of each month); 2) Enrollment falls randomly between Monday and Friday; 3) Follow-up visits follow the visit schedule exactly; 4) Missed visits are distributed uniformly at a rate of 10%; 5) Dropout is 5% per person year and follows an exponential distribution; 6) HIV-infection (in the absence of PrEP) in the placebo group is 4% per person year and follows an exponential distribution; 7) Initiation of DBS sample collection begins by May 2017; 8) Samples are collected and assayed at 6 month intervals, and approximately 3.5 months before each 6-monthly DSMB meeting. Prevalence of FTC/TDF use (either detectable or effective use) was set 1%, 10%, and 20% per person-year. For these simulations, participants are assumed to be either on (or off) FTC/TDF during the entire trial; however the methods for estimating FTC/TDF prevalence are valid and accommodate other extremes such as all participants using PrEP a fraction of the time, or any other pattern of PrEP use.

[figure not shown]
Simulation results are shown in the following figures corresponding to plans that assay samples on 1, 2, or 3 specific days per month. Each figure shows the 95% confidence interval around the FTC/TDF prevalence that would be observed at each 6-monthly DSMB meeting, assuming 1%, 10%, and 20% FTC/TDF prevalence. Below each date is the total number of samples that would be assayed according to the simulation study. Estimates are shown as dots of varying color intensity corresponding to the three PrEP use scenarios. Corresponding color bands are used to show the 95% bootstrap confidence interval for each estimate. The results show that at the 2017 DSMB meetings, there is a modest gain in precision associated with more frequent sampling. However by the 3rd DSMB meeting in July 2018, the gain in precision due to assaying more samples is limited.

The proposed plan is chosen for the following reasons. The gain in precision of the PrEP prevalence estimate from 2018 onwards with twice or three times a month collection does not justify the increase in cost and burden on the sites. During 2017, PrEP prevalence is estimated with less precision given once-monthly vs. twice- or thrice-monthly sampling; however we expect low PrEP prevalence during this time period, and low PrEP prevalence will have minimal impact on placebo-group HIV incidence. Thus, it is acceptable to have less precision for PrEP prevalence estimates early on in the trial.

[figure not shown]
**DBS samples collected 1 times per month
HVTN 702**

**DBS samples collected 2 times per month
HVTN 702**

**DBS samples collected 3 times per month
HVTN 702**

11.4.2 PrEP/PEP monitoring based on self-reported PrEP/PEP data

The number and percentage of participants who self-report PrEP/PEP use will be reported overall and by sex at birth, cross-tabulated by detectable PrEP/PEP use by DBS data. In addition, the number and percentage of males and females who self-report PrEP and PEP use at any point during the study will be tabulated, separately for PrEP and PEP use. Additional information on the number of participants currently using PrEP and the total number of courses of PEP reported by PEP users, each stratified by sex at birth, may be provided during the DSMB open session.

11.4.3 PrEP monitoring based on DBS data

At a given calendar time T (e.g., a fixed date prior to a scheduled DSMB meeting), we are interested in the population-level parameter, percent person-years at-risk for HIV on effective PrEP use between initiation of DBS storage, and time T . Definition of this parameter makes the assumption that we have an assay readout from stored samples that accurately measures effective PrEP use as a binary outcome at the time the sample was drawn; importantly it does not require an accurate measurement of effective PrEP use the day before or for any period of time earlier than the sampling day. In addition to estimating percent person-years on effective PrEP use we define a similar parameter, percent person-years exposed to detectable PrEP using the lower limit of quantitation (LLOQ) of the DBS assay.

Define the target parameter of interest as

$$\Phi(T) = \frac{\int_{T_0}^T p(t) E[Y(t)] dt}{\int_{T_0}^T E[Y(t)] dt}$$

where T_0 is the time since the first person enrolled after DBS storage commenced, $p(t)$ is the percent of participants on effective PrEP use at time $t \in [T_0, T]$, and $E[Y(t)]$ is the expected number of participants with DBS storage at-risk for HIV at time t .

We estimate $\Phi(T)$ based on the binary PrEP use readout from the DBS assay and the DBS sampling plan. Let i ranging from 1 to N index study participants and let j ranging from 1 to M_i index participant serum collection dates that are sampled for assaying. For each sample collected, we have an indicator x_{ij} of effective PrEP use which is only measured if the DBS sampling indicator, Δ_{ij} , is equal to 1. The estimated percent person-years on effective PrEP use from the initiation of PrEP monitoring time T_0 until time T is defined as

$$\hat{\Phi}(T) = \frac{\sum_{i=1}^N \sum_{j=1}^{M_i} \Delta_{ij} x_{ij} \pi_{ij}^{-1} P_{ij}}{\sum_{i=1}^N \sum_{j=1}^{M_i} P_{ij}}$$

where the sampling probability, π_{ij} , and person-years, P_{ij} , are defined below.

Let k ranging from 1 to K index the DBS sampling plan collection intervals $[T_0, T_1]$, $(T_1, T_2]$, \dots , $(T_{K-1}, T_K]$ where the right endpoint of each interval is a sample collection date (with

$T_K \equiv T$) and define \mathcal{T}_k as the k^{th} interval. Let $t_{i1} < t_{i2} < \dots < t_{iM_i}$ be the sampling times in $[T_0, T]$ for the i^{th} participant and define t_{i0} as the maximum of T_0 and the i^{th} participants enrollment time. The DBS sampling plan determines which samples, collectively across participants, will be assayed for PrEP use. Define the set of samples, S_{ij} , as all samples collected during the same collection interval \mathcal{T}_k as the sample i, j . That is, $S_{ij} \equiv \{i', j' | t_{i'j'} \in \mathcal{T}_k \text{ for } k \text{ s.t. } t_{ij} \in \mathcal{T}_k\}$. Define the sampling probability as

$$\pi_{ij} \equiv \frac{\sum_{i', j' \in S_{ij}} \Delta_{i'j'}}{|S_{ij}|}$$

where $|S_{ij}|$ is the number of samples in set S_{ij} . Define person-years, P_{ij} , as $t_{ij} - t_{i(j-1)}$. We will report bootstrap 95% confidence intervals for $\Phi(T)$. The same approach is used for point and confidence interval estimation of the percent person-years exposed to detectable PrEP use. An example of PrEP use report statistics are shown in Table 4.

Table 4: Estimated rates of PrEP use and estimated percent person-years on effective PrEP use

Number of DBS specimens collected over the 1 st batch period	N_1
Number of DBS specimens assayed over the 1 st batch period	N_2
Proportion of assayed specimens with TFV-DP above LLOQ (95% CI)	N_3/N_2 (x.xx, x.xx)
Proportion of assayed specimens with TFV-DP above effective use threshold* (95% CI)	N_4/N_2 (x.xx, x.xx)
Percent person years on detectable PrEP through date T=xx (95% CI) [#]	$\widehat{\Phi}(T)_d$ (x.xx, x.xx)
Percent person years on effective PrEP through date T=xx (95% CI) [#]	$\widehat{\Phi}(T)_e$ (x.xx, x.xx)
Repeat through N th batch period	

*threshold defined by sex-at-birth (700 fmol/punch in men, 1000 fmol/punch in women)

[#] $\widehat{\Phi}(T)_d$ is an estimate of the target parameter of interest based on measured TFV-DP above the LLOQ. Similarly, $\widehat{\Phi}(T)_e$ is based on TFV-DP above the study specific threshold for effective PrEP use.

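### The bootstrap interval for percent person-years on PrEP is (0.00, 0.00) when no assayed specimen is positive, and under-covers in early and by-arm reports at about 1% use or less

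*SAP*

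**What the plan says.** SAP 11.4.3 estimates the percent of at-risk person-years on effective PrEP from binary dried-blood-spot (DBS) readouts. The numerator adds person-time divided by sampling probability over assayed specimens that are positive. The denominator is all person-time. For uncertainty it says "We will report bootstrap 95% confidence intervals for" this parameter, and then: "The same approach is used for point and confidence interval estimation of the percent person-years exposed to detectable PrEP use". It names no bootstrap type, no resampling unit and no rule for the case of no positive specimen.

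The setting is one of few specimens and rare use:

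- SAP 11.4.1 plans on "collecting DBS samples on 1 day each month".
- Its simulation scenarios are given as: "Prevalence of FTC/TDF use (either detectable or effective use) was set 1%, 10%, and 20% per person-year". The bands drawn for them are bootstrap intervals: "Corresponding color bands are used to show the 95% bootstrap confidence interval for each estimate".
- For 2017 it says "we expect low PrEP prevalence during this time period", and it accepts lower precision early in the trial on that ground.
- SAP 11.4 says "measures of PrEP use will be reported by treatment arm to the DSMB", which halves the specimens behind each interval. The Oversight Group and protocol leadership see pooled estimates.

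Elsewhere the documents treat small counts differently. Protocol 6.4.2 attaches an upper limit of 0.14% to zero events in 2700, and SAP 10.6 uses exact intervals for immune response rates.

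**The concern.** A bootstrap can only reproduce variation that is present in the sample. If no assayed specimen is positive, every resample is also all negative, so the interval has zero width whatever the sample size. The early, by-arm, low-prevalence reports are where this is most likely. Effective use is a subset of detectable use, so it is rarer still.

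Accepting lower precision early on does not cover this. Lower precision should appear as a wide interval. Here the interval is too narrow or has no width, so the imprecision the SAP accepts is hidden from its readers. At stake is the accuracy of what the DSMB and Oversight Group are told about PrEP use, which is shown beside the other measures of trial under-performance.

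**Working it through.** **Benchmark.** Protocol 6.4.2 gives 0.14% for 0 of 2700. The exact (Clopper-Pearson) upper limit at zero events is 1 − 0.025^(1/n). At n = 2700 this is 0.1365%, which reproduces the stated figure. No numeric PrEP interval can be read in SAP 11.4, so there is none to reproduce there.

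**Zero positives.** If every assayed readout is 0, the numerator is 0 in the data and in every resample. Percentile, basic and normal bootstrap intervals are all (0.00, 0.00), and BCa is undefined. This needs no assumption about sample size. The exact upper limits on the unweighted scale would be:

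- 0 of 146: 1 − 0.025^(1/146) = 2.5%
- 0 of 73: 1 − 0.025^(1/73) = 4.9%

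**Coverage, unweighted.** Let K be the number of positives among n independent specimens, K ~ Binomial(n, p). The percentile limits are the 2.5% and 97.5% quantiles of Binomial(n, K/n), divided by n. Coverage is the probability of those K whose interval contains p.

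Take p = 1% and n = 100. K = 0 gives (0, 0) and misses. K = 1 gives (0, 3%) and K = 5 gives (1%, 10%), both of which contain 1%. K = 6 gives (2%, 11%) and misses. Coverage is therefore P(1 ≤ K ≤ 5) = 63%. P(K = 0) = 0.99^100 = 37%, so nearly all of the shortfall is the zero-width case.

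**Coverage, weighted.** A Monte Carlo check used a person-time-weighted ratio like the SAP's and a participant-level percentile bootstrap (1500 replicates, 600 resamples). Visit-interval weights and one or two specimens per participant were assumed. Results at 1% true use:

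| Assayed n | P(no positive) | Unweighted coverage | Weighted coverage |
|---|---|---|---|
| 50 | 60% | 39% | 40% |
| 100 | 37% | 63% | 57% |
| 200 | 13% | 87% | 76% |
| 300 | 5% | 95% | not run |
| 400 | 2% | 91% | 87% |
| 500 | 0.7% | 95% | not run |

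The weighted version also misses when there are a few positives. At n = 200 its simulated zero-positive rate was 12.5%, so the further misses are 100 − 75.5 − 12.5 = 12 points. At n = 100 they are 100 − 56.5 − 37.4 = 6 points.

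Weighted coverage at n = 100, 200 and 400 was 41%, 56% and 71% at 0.5% true use, and 75%, 89% and 91% at 2%. At 10% and 20% use, unweighted percentile coverage is about 94% to 97% from n = 100 upward.

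**Which n applies.** The SAP's counts are in figures that are not shown, so these are assumed. With the SAP 11.4.1 conditions, the design enrolment pattern in protocol 6.4.1 and a study opening between October 2016 and January 2017, the cumulative pooled counts are:

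| Through | Pooled specimens | One arm (half) |
|---|---|---|
| End June 2017 | 16–139 | 8–70 |
| End Sept 2017 | 91–232 | 46–116 |
| End Dec 2017 | 211–427 | 106–214 |
| Mid-March 2018 | 270–706 | 135–353 |
| Sept 2018 | 780–1060 | 390–530 |

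On these counts, the 2017 by-arm intervals at 1% use have unweighted coverage of at most about 87%, and much less at the lower end. By late 2018 the pooled reports are near nominal.

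**The case against.** The strongest reply is that nothing turns on this interval. The enrolment and futility guidelines in SAP 11.3 rest on the probability of reaching 256 or 93 infections. No PrEP threshold and no between-arm PrEP test is planned, and SAP 11.4 describes the collection as a precaution.

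The hidden uncertainty also lies where it matters little for power. If 4.9% of person-years were on fully effective PrEP, placebo incidence would fall from 4.0% to 4.0 × (1 − 0.049) = 3.8%. Protocol Table 6-3 gives power of 91% at 4.0% and 86% at 3.5%, so the loss is about 2 points by linear interpolation. At 10% or 20% use the bootstrap works. All of this stands, and it limits the consequence. It does not make a zero-width 95% interval correct.

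Three stronger readings are tempting, and the documents do not support them:

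- **That the bands at 1% undermine once-monthly collection.** SAP 11.4.1 rests that choice on the small gain in precision from 2018 onward, set against cost and site burden. For 2017 it relies on low use having little effect on incidence. Neither argument needs nominal coverage of the early 1% bands.
- **That every interval in SAP Table 4 is a bootstrap.** The bootstrap sentence covers the person-years parameters. The method for the specimen proportions is not stated.
- **That the DSMB would read (0.00, 0.00) as proof of no use.** Table 4 also shows the number assayed and the raw proportions, and SAP 11.4.2 cross-tabulates self-report against DBS results. A careful reader could see the small denominator.

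**Conclusion.** The point holds within limits. The collapse to (0.00, 0.00) at zero positives is certain for any nonparametric bootstrap. The under-coverage is substantial at about 1% use or less with up to roughly 200 assayed specimens, and it largely disappears by several hundred. At 0.5% use it lasts longer.

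The size rests on three assumptions: the specimen counts, the 1% scenario (the SAP gives no number for the low use it expects), and a percentile bootstrap. Basic and normal bootstrap intervals do no better: 18% to 87% for n from 20 to 200, 80% at n = 300, and 87% to 93% for n from 500 to 1400.

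The consequence is misleading monitoring information in early and by-arm reports. The efficacy analysis and all stopping and enrolment guidelines are untouched. Since DSMB monitoring ended on 23 January 2020, those reports cannot be changed. The correction now matters for any final estimate of PrEP use under protocol exploratory objective 5, and for re-use of this monitoring template. It is a minor but real correction.

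**What to change.** In SAP 11.4.3, replace the bootstrap for both person-years parameters, pooled and by arm, with the gamma (Fay-Feuer) interval for a weighted sum. Aggregate weights by participant, because repeated specimens from one person are not independent. Using it in every report avoids having to define how many positives are enough for the bootstrap. At a minimum, use it whenever positives are few.

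State the zero-positive rule explicitly: report 0 with a non-zero upper limit. For the gamma interval that limit is half the 97.5% point of chi-square on 2 degrees of freedom, 7.378 / 2 = 3.69, times the largest participant weight. With equal weights of 1/n this is 3.69/146 = 2.5% and 3.69/73 = 5.1%, close to the exact 2.5% and 4.9%. With unequal weights it is larger.

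In Table 4, name Clopper-Pearson for the specimen proportions.

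The cost is a short SAP paragraph, a few lines of code, and wider, somewhat conservative early intervals. In a simulation under design enrolment with DBS assumed to start at month 6, the gamma interval covered 98% to 100%. Its mean pooled upper limit was about 6% after six collection days at 1% true use. Aggregation by participant only approximates independent counts, so the exact form adopted should be checked by simulation before use.

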11.5 Performance Standards for Quality of Trial Conduct

The protocol team and study investigators will have performance standards regarding the quality of trial conduct in addition to the study event rate. Some of these standards will relate to achievement of targeted levels of:

1. Participant enrollment into the trial (targets based on protocol assumptions);
2. Adherence to study interventions (target 95% adherence, with minimally acceptable level of 80%);
3. Retention of participants (target 5% annual dropout or less, with minimally acceptable level of no more than 10% annual dropout).

The DSMB and the HVTN 702 leadership will monitor whether the trial is achieving at least minimally acceptable levels of key performance standards. The DSMB will make recommendations to improve areas that are deficient. Termination of the trial would be considered if it appears unlikely that minimally acceptable performance will be achieved.

12 Statistical Software

All analyses described in this SAP will be conducted in *R* and *SAS*.

13 Roles of study statisticians

HVTN SDMC statisticians will be blinded or unblinded to study treatment. During protocol development and after primary follow-up is completed, there will be no distinction between the roles; both types of statisticians will be responsible for designing and analyzing the study. During the primary follow-up period, however, only the unblinded statisticians will see interim data broken down by treatment arm. Their role will be to conduct the interim monitoring and to produce and present reports on accruing data to the study DSMB. During the primary follow-up period, blinded statisticians will see only the interim data pooled across treatment arms. This way, blinded statisticians can assist protocol leadership in making decisions about modifications to the protocol without being influenced by interim efficacy results.

REFERENCES

- AALEN O. (1978). Nonparametric Estimation of Partial Transition-Probabilities in Multiple Decrement Models. *Ann Stat.* **6(3)**: 534–45.
- BENKESER, D., CARONE, M., GILBERT, P. Improved Estimation of the Cumulative Incidence of Rare Outcomes. *Stat Med.* **37(2)**: 280-293.

Appendix

- DSMB open session table shells
- DSMB closed session table shells

DRAFT

HVTN 702

**Data and Safety Monitoring Board (DSMB)
OPEN Report
All Tables**

Tables and Figures

Table ENROLL1. Enrollment by Study Site	2
Table ENROLL2. Disposition of Study Participants – Overall and by Study Site*.....	3
Table BL1. Baseline Participant Characteristics – Overall and by Study Site	4
Table BL2. Baseline Risk Behaviors for Females – Overall and by Study Site	5
Table BL3. Baseline Risk Behaviors for Males – Overall and by Study Site.....	6
Table STATUS1. Study Status and Reasons for Early Study Termination – Overall and by Study Site	7
Table STATUS2. Vaccination Status and Reasons for Discontinuation – Overall and by Study Site	8
Table RETEN1. Visit Retention – Overall and by Study Site	9
Table RETEN2. Vaccination Adherence – Overall and by Study Site.....	10
Table RE1. Maximum Local Reactogenicity Summary by Vaccination	11
Table RE2. Maximum Systemic Reactogenicity Summary by Vaccination	12
Table EAE1. Expedited Adverse Events (EAEs) Reported to the Regulatory Support Center (RSC) by Participant and Decreasing Severity	13
Table AE1. Grade 2-5 Adverse Events (AEs) by System Organ Class, Sorted by Decreasing Frequency	14
Table AE2. Grade 2-5 Adverse Events (AEs) by System Organ Class, High Level Term, and Severity.....	15
Table AE3. Grade 2-5 Adverse Events (AEs) Related to Study Product by System Organ Class, High Level Term, and Severity	16
Table SI1. Social Impact Summary of Events	17
Table SI2. Social Impact Summary at Participant Level	18
Table PREG1. Pregnancy Listing.....	19

HVTN 702: A phase 2b/3 trial of ALVAC/gp120+MF59 vs. Placebo in South Africa
Open Report for DSMB meeting on [Date]. Data cutoff date: [Date].

Table ENROLL1. Enrollment by Study Site

Duration of accrual calculated as activation date through [Date].

Site*	Target	Total Enrolled	Activation Date	First Enrollment Date	Most Recent Enrollment Date	Duration of Accrual (Weeks)	Average per week
Brits	xxx	xxx	ddMMMyyyy	ddMMMyyyy	ddMMMyyyy	xxx.x	x.x
Cape Town - Emavundleni	xxx	xxx	ddMMMyyyy	ddMMMyyyy	ddMMMyyyy	xxx.x	x.x
Cape Town - Khayelitsha	xxx	xxx	ddMMMyyyy	ddMMMyyyy	ddMMMyyyy	xxx.x	x.x
Durban - eThekweni	xxx	xxx	ddMMMyyyy	ddMMMyyyy	ddMMMyyyy	xxx.x	x.x
Durban - Isipingo	xxx	xxx	ddMMMyyyy	ddMMMyyyy	ddMMMyyyy	xxx.x	x.x
Durban - Verulam	xxx	xxx	ddMMMyyyy	ddMMMyyyy	ddMMMyyyy	xxx.x	x.x
Klerksdorp	xxx	xxx	ddMMMyyyy	ddMMMyyyy	ddMMMyyyy	xxx.x	x.x
Ladysmith	xxx	xxx	ddMMMyyyy	ddMMMyyyy	ddMMMyyyy	xxx.x	x.x
Medunsa	xxx	xxx	ddMMMyyyy	ddMMMyyyy	ddMMMyyyy	xxx.x	x.x
Mthatha	xxx	xxx	ddMMMyyyy	ddMMMyyyy	ddMMMyyyy	xxx.x	x.x
Rustenburg	xxx	xxx	ddMMMyyyy	ddMMMyyyy	ddMMMyyyy	xxx.x	x.x
Soshanguve	xxx	xxx	ddMMMyyyy	ddMMMyyyy	ddMMMyyyy	xxx.x	x.x
Soweto - Bara	xxx	xxx	ddMMMyyyy	ddMMMyyyy	ddMMMyyyy	xxx.x	x.x
Soweto - Kliptown	xxx	xxx	ddMMMyyyy	ddMMMyyyy	ddMMMyyyy	xxx.x	x.x
Tembisa	xxx	xxx	ddMMMyyyy	ddMMMyyyy	ddMMMyyyy	xxx.x	x.x
	xxxx	xxxx	ddMMMyyyy	ddMMMyyyy	ddMMMyyyy	xxx.x	xx.x

Sites shown ordered alphabetically.

*Only activated sites are included

HVTN 702: A phase 2b/3 trial of ALVAC/gp120+MF59 vs. Placebo in South Africa
Open Report for DSMB meeting on [Date]. Data cutoff date: [Date].

Table ENROLL2. Disposition of Study Participants – Overall and by Study Site

	Total	Soweto - Bara	Soshanguve	Durban - Verulam	Cape Town - Emavundleni	Tembisa	Cape Town - Khayelitsha
Number Randomized	xxx (xx.x%)	xxx (xx.x%)	xxx (xx.x%)	xxx (xx.x%)	xxx (xx.x%)	xxx (xx.x%)	xxx (xx.x%)
Enrolled*	xxx (xx.x%)	xxx (xx.x%)	xxx (xx.x%)	xxx (xx.x%)	xxx (xx.x%)	xxx (xx.x%)	xxx (xx.x%)
Not Enrolled	xxx (xx.x%)	xxx (xx.x%)	xxx (xx.x%)	xxx (xx.x%)	xxx (xx.x%)	xxx (xx.x%)	xxx (xx.x%)
Pending Enrollment	xxx (xx.x%)	xxx (xx.x%)	xxx (xx.x%)	xxx (xx.x%)	xxx (xx.x%)	xxx (xx.x%)	xxx (xx.x%)
Number Enrolled*	xxx (xx.x%)	xxx (xx.x%)	xxx (xx.x%)	xxx (xx.x%)	xxx (xx.x%)	xxx (xx.x%)	xxx (xx.x%)
On Study	xxx (xx.x%)	xxx (xx.x%)	xxx (xx.x%)	xxx (xx.x%)	xxx (xx.x%)	xxx (xx.x%)	xxx (xx.x%)
Completed Study	xxx (xx.x%)	xxx (xx.x%)	xxx (xx.x%)	xxx (xx.x%)	xxx (xx.x%)	xxx (xx.x%)	xxx (xx.x%)
Off Study Early	xxx (xx.x%)	xxx (xx.x%)	xxx (xx.x%)	xxx (xx.x%)	xxx (xx.x%)	xxx (xx.x%)	xxx (xx.x%)

*Enrolled implies receipt of the first vaccination.

HIV-infected participants who have completed follow-up are reported as On Study, in order to obscure their numbers.

HVTN 702: A phase 2b/3 trial of ALVAC/gp120+MF59 vs. Placebo in South Africa
Open Report for DSMB meeting on [Date]. Data cutoff date: [Date].

Table BL1. Baseline Participant Characteristics – Overall and by Study Site

	Total	Soweto - Bara	Soshanguve	Durban - Verulam	Cape Town - Emavundleni	Tembisa	Cape Town - Khayelitsha
Total Enrolled	xxx (xx.x%)	xxx (xx.x%)	xxx (xx.x%)	xxx (xx.x%)	xxx (xx.x%)	xxx (xx.x%)	xxx (xx.x%)
Sex at Birth							
Male	xxx (xx.x%)	xxx (xx.x%)	xxx (xx.x%)	xxx (xx.x%)	xxx (xx.x%)	xxx (xx.x%)	xxx (xx.x%)
Female	xxx (xx.x%)	xxx (xx.x%)	xxx (xx.x%)	xxx (xx.x%)	xxx (xx.x%)	xxx (xx.x%)	xxx (xx.x%)
Gender Identity [^]							
Male	xxx (xx.x%)	xxx (xx.x%)	xxx (xx.x%)	xxx (xx.x%)	xxx (xx.x%)	xxx (xx.x%)	xxx (xx.x%)
Female	xxx (xx.x%)	xxx (xx.x%)	xxx (xx.x%)	xxx (xx.x%)	xxx (xx.x%)	xxx (xx.x%)	xxx (xx.x%)
Transgender Male	xxx (xx.x%)	xxx (xx.x%)	xxx (xx.x%)	xxx (xx.x%)	xxx (xx.x%)	xxx (xx.x%)	xxx (xx.x%)
Transgender Female	xxx (xx.x%)	xxx (xx.x%)	xxx (xx.x%)	xxx (xx.x%)	xxx (xx.x%)	xxx (xx.x%)	xxx (xx.x%)
Gender Variant	xxx (xx.x%)	xxx (xx.x%)	xxx (xx.x%)	xxx (xx.x%)	xxx (xx.x%)	xxx (xx.x%)	xxx (xx.x%)
Self-identify	xxx (xx.x%)	xxx (xx.x%)	xxx (xx.x%)	xxx (xx.x%)	xxx (xx.x%)	xxx (xx.x%)	xxx (xx.x%)
Prefer Not to Answer	xxx (xx.x%)	xxx (xx.x%)	xxx (xx.x%)	xxx (xx.x%)	xxx (xx.x%)	xxx (xx.x%)	xxx (xx.x%)
Age (Years)							
18 – 20	xxx (xx.x%)	xxx (xx.x%)	xxx (xx.x%)	xxx (xx.x%)	xxx (xx.x%)	xxx (xx.x%)	xxx (xx.x%)
21 – 30	xxx (xx.x%)	xxx (xx.x%)	xxx (xx.x%)	xxx (xx.x%)	xxx (xx.x%)	xxx (xx.x%)	xxx (xx.x%)
31 – 40	xxx (xx.x%)	xxx (xx.x%)	xxx (xx.x%)	xxx (xx.x%)	xxx (xx.x%)	xxx (xx.x%)	xxx (xx.x%)
Median (Min, Max)	xx (xx, xx)	xx (xx, xx)	xx (xx, xx)	xx (xx, xx)	xx (xx, xx)	xx (xx, xx)	xx (xx, xx)
Race							
White	xxx (xx.x%)	xxx (xx.x%)	xxx (xx.x%)	xxx (xx.x%)	xxx (xx.x%)	xxx (xx.x%)	xxx (xx.x%)
Black or African American	xxx (xx.x%)	xxx (xx.x%)	xxx (xx.x%)	xxx (xx.x%)	xxx (xx.x%)	xxx (xx.x%)	xxx (xx.x%)
Asian	xxx (xx.x%)	xxx (xx.x%)	xxx (xx.x%)	xxx (xx.x%)	xxx (xx.x%)	xxx (xx.x%)	xxx (xx.x%)
Indian	xxx (xx.x%)	xxx (xx.x%)	xxx (xx.x%)	xxx (xx.x%)	xxx (xx.x%)	xxx (xx.x%)	xxx (xx.x%)
Colored/Mixed	xxx (xx.x%)	xxx (xx.x%)	xxx (xx.x%)	xxx (xx.x%)	xxx (xx.x%)	xxx (xx.x%)	xxx (xx.x%)
Other	xxx (xx.x%)	xxx (xx.x%)	xxx (xx.x%)	xxx (xx.x%)	xxx (xx.x%)	xxx (xx.x%)	xxx (xx.x%)
Multi-racial	xxx (xx.x%)	xxx (xx.x%)	xxx (xx.x%)	xxx (xx.x%)	xxx (xx.x%)	xxx (xx.x%)	xxx (xx.x%)

[^]Participants may self-report more than one gender identity, thus numbers may total to more than 100%.

HVTN 702: A phase 2b/3 trial of ALVAC/gp120+MF59 vs. Placebo in South Africa
Open Report for DSMB meeting on [Date]. Data cutoff date: [Date].

Table BL2. Baseline Risk Behaviors for Females – Overall and by Study Site

	Total	Soweto - Bara	Soshanguve	Durban - Verulam	Cape Town - Emavundleni	Tembisa	Cape Town - Khayelitsha
Total Enrolled	xxx (xx.x%)	xxx (xx.x%)	xxx (xx.x%)	xxx (xx.x%)	xxx (xx.x%)	xxx (xx.x%)	xxx (xx.x%)
Number Sex Partners in the Last Month							
0	xxx (xx.x%)	xxx (xx.x%)	xxx (xx.x%)	xxx (xx.x%)	xxx (xx.x%)	xxx (xx.x%)	xxx (xx.x%)
1	xxx (xx.x%)	xxx (xx.x%)	xxx (xx.x%)	xxx (xx.x%)	xxx (xx.x%)	xxx (xx.x%)	xxx (xx.x%)
2	xxx (xx.x%)	xxx (xx.x%)	xxx (xx.x%)	xxx (xx.x%)	xxx (xx.x%)	xxx (xx.x%)	xxx (xx.x%)
3-4	xxx (xx.x%)	xxx (xx.x%)	xxx (xx.x%)	xxx (xx.x%)	xxx (xx.x%)	xxx (xx.x%)	xxx (xx.x%)
>=5	xxx (xx.x%)	xxx (xx.x%)	xxx (xx.x%)	xxx (xx.x%)	xxx (xx.x%)	xxx (xx.x%)	xxx (xx.x%)
Median (Min, Max)	xx (xx, xx)	xx (xx, xx)	xx (xx, xx)	xx (xx, xx)	xx (xx, xx)	xx (xx, xx)	xx (xx, xx)
Condom use							
Always	xxx (xx.x%)	xxx (xx.x%)	xxx (xx.x%)	xxx (xx.x%)	xxx (xx.x%)	xxx (xx.x%)	xxx (xx.x%)
Sometimes	xxx (xx.x%)	xxx (xx.x%)	xxx (xx.x%)	xxx (xx.x%)	xxx (xx.x%)	xxx (xx.x%)	xxx (xx.x%)
Never	xxx (xx.x%)	xxx (xx.x%)	xxx (xx.x%)	xxx (xx.x%)	xxx (xx.x%)	xxx (xx.x%)	xxx (xx.x%)
Anal Sex							
Yes	xxx (xx.x%)	xxx (xx.x%)	xxx (xx.x%)	xxx (xx.x%)	xxx (xx.x%)	xxx (xx.x%)	xxx (xx.x%)
Had an HIV+ Partner							
Yes	xxx (xx.x%)	xxx (xx.x%)	xxx (xx.x%)	xxx (xx.x%)	xxx (xx.x%)	xxx (xx.x%)	xxx (xx.x%)
Unprotected Sex with HIV+ Partner							
Yes	xxx (xx.x%)	xxx (xx.x%)	xxx (xx.x%)	xxx (xx.x%)	xxx (xx.x%)	xxx (xx.x%)	xxx (xx.x%)
Exchange of Sex for Money/Gifts							
Yes	xxx (xx.x%)	xxx (xx.x%)	xxx (xx.x%)	xxx (xx.x%)	xxx (xx.x%)	xxx (xx.x%)	xxx (xx.x%)
Diagnosed with or treated for an STI							
Yes	xxx (xx.x%)	xxx (xx.x%)	xxx (xx.x%)	xxx (xx.x%)	xxx (xx.x%)	xxx (xx.x%)	xxx (xx.x%)
Alcohol Use and Unprotected Sex							
Never	xxx (xx.x%)	xxx (xx.x%)	xxx (xx.x%)	xxx (xx.x%)	xxx (xx.x%)	xxx (xx.x%)	xxx (xx.x%)
1-2 times	xxx (xx.x%)	xxx (xx.x%)	xxx (xx.x%)	xxx (xx.x%)	xxx (xx.x%)	xxx (xx.x%)	xxx (xx.x%)
3-5 times	xxx (xx.x%)	xxx (xx.x%)	xxx (xx.x%)	xxx (xx.x%)	xxx (xx.x%)	xxx (xx.x%)	xxx (xx.x%)
6 or more times	xxx (xx.x%)	xxx (xx.x%)	xxx (xx.x%)	xxx (xx.x%)	xxx (xx.x%)	xxx (xx.x%)	xxx (xx.x%)

Participants are not required to answer risk behavior questions, thus numbers and percentages may not total 100% of enrolled participants.

HVTN 702: A phase 2b/3 trial of ALVAC/gp120+MF59 vs. Placebo in South Africa
Open Report for DSMB meeting on [Date]. Data cutoff date: [Date].

Table BL3. Baseline Risk Behaviors for Males – Overall and by Study Site

	Total	Soweto - Bara	Soshanguve	Durban - Verulam	Cape Town - Emavundleni	Tembisa	Cape Town - Khayelitsha
Total Enrolled	xxx (xx.x%)	xxx (xx.x%)	xxx (xx.x%)	xxx (xx.x%)	xxx (xx.x%)	xxx (xx.x%)	xxx (xx.x%)
Number Sex Partners in the Last Month							
0	xxx (xx.x%)	xxx (xx.x%)	xxx (xx.x%)	xxx (xx.x%)	xxx (xx.x%)	xxx (xx.x%)	xxx (xx.x%)
1	xxx (xx.x%)	xxx (xx.x%)	xxx (xx.x%)	xxx (xx.x%)	xxx (xx.x%)	xxx (xx.x%)	xxx (xx.x%)
2	xxx (xx.x%)	xxx (xx.x%)	xxx (xx.x%)	xxx (xx.x%)	xxx (xx.x%)	xxx (xx.x%)	xxx (xx.x%)
3-4	xxx (xx.x%)	xxx (xx.x%)	xxx (xx.x%)	xxx (xx.x%)	xxx (xx.x%)	xxx (xx.x%)	xxx (xx.x%)
>=5	xxx (xx.x%)	xxx (xx.x%)	xxx (xx.x%)	xxx (xx.x%)	xxx (xx.x%)	xxx (xx.x%)	xxx (xx.x%)
Median (Min, Max)	xx (xx, xx)	xx (xx, xx)	xx (xx, xx)	xx (xx, xx)	xx (xx, xx)	xx (xx, xx)	xx (xx, xx)
Condom use							
Always	xxx (xx.x%)	xxx (xx.x%)	xxx (xx.x%)	xxx (xx.x%)	xxx (xx.x%)	xxx (xx.x%)	xxx (xx.x%)
Sometimes	xxx (xx.x%)	xxx (xx.x%)	xxx (xx.x%)	xxx (xx.x%)	xxx (xx.x%)	xxx (xx.x%)	xxx (xx.x%)
Never	xxx (xx.x%)	xxx (xx.x%)	xxx (xx.x%)	xxx (xx.x%)	xxx (xx.x%)	xxx (xx.x%)	xxx (xx.x%)
Anal Sex							
Yes	xxx (xx.x%)	xxx (xx.x%)	xxx (xx.x%)	xxx (xx.x%)	xxx (xx.x%)	xxx (xx.x%)	xxx (xx.x%)
Had an HIV+ Partner							
Yes	xxx (xx.x%)	xxx (xx.x%)	xxx (xx.x%)	xxx (xx.x%)	xxx (xx.x%)	xxx (xx.x%)	xxx (xx.x%)
Unprotected Sex with HIV+ Partner							
Yes	xxx (xx.x%)	xxx (xx.x%)	xxx (xx.x%)	xxx (xx.x%)	xxx (xx.x%)	xxx (xx.x%)	xxx (xx.x%)
Exchange of Sex for Money/Gifts							
Yes	xxx (xx.x%)	xxx (xx.x%)	xxx (xx.x%)	xxx (xx.x%)	xxx (xx.x%)	xxx (xx.x%)	xxx (xx.x%)
Diagnosed with or treated for an STI							
Yes	xxx (xx.x%)	xxx (xx.x%)	xxx (xx.x%)	xxx (xx.x%)	xxx (xx.x%)	xxx (xx.x%)	xxx (xx.x%)
Alcohol Use and Unprotected Sex							
Never	xxx (xx.x%)	xxx (xx.x%)	xxx (xx.x%)	xxx (xx.x%)	xxx (xx.x%)	xxx (xx.x%)	xxx (xx.x%)
1-2 times	xxx (xx.x%)	xxx (xx.x%)	xxx (xx.x%)	xxx (xx.x%)	xxx (xx.x%)	xxx (xx.x%)	xxx (xx.x%)
3-5 times	xxx (xx.x%)	xxx (xx.x%)	xxx (xx.x%)	xxx (xx.x%)	xxx (xx.x%)	xxx (xx.x%)	xxx (xx.x%)
6 or more times	xxx (xx.x%)	xxx (xx.x%)	xxx (xx.x%)	xxx (xx.x%)	xxx (xx.x%)	xxx (xx.x%)	xxx (xx.x%)

Participants are not required to answer risk behavior questions, thus numbers and percentages may not total 100% of enrolled participants.

HVTN 702: A phase 2b/3 trial of ALVAC/gp120+MF59 vs. Placebo in South Africa
Open Report for DSMB meeting on [Date]. Data cutoff date: [Date].

Table STATUS1. Study Status and Reasons for Early Study Termination – Overall and by Study Site

	Total		Soweto - Bara		Soshanguve		Durban - Verulam		Cape Town - Emavundleni		Tembisa		Cape Town - Khayelitsha	
Total Enrolled	xxx	(xx.x%)	xxx	(xx.x%)	xxx	(xx.x%)	xxx	(xx.x%)	xxx	(xx.x%)	xxx	(xx.x%)	xxx	(xx.x%)
Status*														
On Study, In Trt Phase	xxx	(xx.x%)	xxx	(xx.x%)	xxx	(xx.x%)	xxx	(xx.x%)	xxx	(xx.x%)	xxx	(xx.x%)	xxx	(xx.x%)
On Study, Completed Trt Phase	xxx	(xx.x%)	xxx	(xx.x%)	xxx	(xx.x%)	xxx	(xx.x%)	xxx	(xx.x%)	xxx	(xx.x%)	xxx	(xx.x%)
On Study, Discontinued Trt	xxx	(xx.x%)	xxx	(xx.x%)	xxx	(xx.x%)	xxx	(xx.x%)	xxx	(xx.x%)	xxx	(xx.x%)	xxx	(xx.x%)
Completed Study, Completed Trt Phas	xxx	(xx.x%)	xxx	(xx.x%)	xxx	(xx.x%)	xxx	(xx.x%)	xxx	(xx.x%)	xxx	(xx.x%)	xxx	(xx.x%)
Completed Study, Discontinued Trt	xxx	(xx.x%)	xxx	(xx.x%)	xxx	(xx.x%)	xxx	(xx.x%)	xxx	(xx.x%)	xxx	(xx.x%)	xxx	(xx.x%)
Off Study Early, Completed Trt Phase	xxx	(xx.x%)	xxx	(xx.x%)	xxx	(xx.x%)	xxx	(xx.x%)	xxx	(xx.x%)	xxx	(xx.x%)	xxx	(xx.x%)
Off Study Early, Discontinued Trt	xxx	(xx.x%)	xxx	(xx.x%)	xxx	(xx.x%)	xxx	(xx.x%)	xxx	(xx.x%)	xxx	(xx.x%)	xxx	(xx.x%)
Reasons for Early Study Termination	xxx	(xx.x%)	xxx	(xx.x%)	xxx	(xx.x%)	xxx	(xx.x%)	xxx	(xx.x%)	xxx	(xx.x%)	xxx	(xx.x%)
Death	xxx	(xx.x%)	xxx	(xx.x%)	xxx	(xx.x%)	xxx	(xx.x%)	xxx	(xx.x%)	xxx	(xx.x%)	xxx	(xx.x%)
Participant refused further participation	xxx	(xx.x%)	xxx	(xx.x%)	xxx	(xx.x%)	xxx	(xx.x%)	xxx	(xx.x%)	xxx	(xx.x%)	xxx	(xx.x%)
Unable to adhere to visit schedule	xxx	(xx.x%)	xxx	(xx.x%)	xxx	(xx.x%)	xxx	(xx.x%)	xxx	(xx.x%)	xxx	(xx.x%)	xxx	(xx.x%)
Participant relocated	xxx	(xx.x%)	xxx	(xx.x%)	xxx	(xx.x%)	xxx	(xx.x%)	xxx	(xx.x%)	xxx	(xx.x%)	xxx	(xx.x%)
Unable to contact	xxx	(xx.x%)	xxx	(xx.x%)	xxx	(xx.x%)	xxx	(xx.x%)	xxx	(xx.x%)	xxx	(xx.x%)	xxx	(xx.x%)
Investigator decision	xxx	(xx.x%)	xxx	(xx.x%)	xxx	(xx.x%)	xxx	(xx.x%)	xxx	(xx.x%)	xxx	(xx.x%)	xxx	(xx.x%)
Inappropriate enrollment	xxx	(xx.x%)	xxx	(xx.x%)	xxx	(xx.x%)	xxx	(xx.x%)	xxx	(xx.x%)	xxx	(xx.x%)	xxx	(xx.x%)
Duplicate screening/enrollment	xxx	(xx.x%)	xxx	(xx.x%)	xxx	(xx.x%)	xxx	(xx.x%)	xxx	(xx.x%)	xxx	(xx.x%)	xxx	(xx.x%)
Early study closure	xxx	(xx.x%)	xxx	(xx.x%)	xxx	(xx.x%)	xxx	(xx.x%)	xxx	(xx.x%)	xxx	(xx.x%)	xxx	(xx.x%)
Participant incarcerated	xxx	(xx.x%)	xxx	(xx.x%)	xxx	(xx.x%)	xxx	(xx.x%)	xxx	(xx.x%)	xxx	(xx.x%)	xxx	(xx.x%)
Other	xxx	(xx.x%)	xxx	(xx.x%)	xxx	(xx.x%)	xxx	(xx.x%)	xxx	(xx.x%)	xxx	(xx.x%)	xxx	(xx.x%)
Early Study Termination Due to an AE	xxx	(xx.x%)	xxx	(xx.x%)	xxx	(xx.x%)	xxx	(xx.x%)	xxx	(xx.x%)	xxx	(xx.x%)	xxx	(xx.x%)

*Participants who discontinued treatment due to HIV infection are reported as 'In Trt Phase' or 'Completed Trt Phase' in order to obscure their numbers.

HVTN 702: A phase 2b/3 trial of ALVAC/gp120+MF59 vs. Placebo in South Africa
Open Report for DSMB meeting on [Date]. Data cutoff date: [Date].

Table STATUS2. Vaccination Status and Reasons for Discontinuation – Overall and by Study Site

	Total	Soweto - Bara	Soshanguve	Durban - Verulam	Cape Town - Emavundleni	Tembisa	Cape Town - Khayelitsha
Vaccination Status							
In Trt Phase ¹	xxx (xx.x%)	xxx (xx.x%)	xxx (xx.x%)	xxx (xx.x%)	xxx (xx.x%)	xxx (xx.x%)	xxx (xx.x%)
Completed Trt Phase	xxx (xx.x%)	xxx (xx.x%)	xxx (xx.x%)	xxx (xx.x%)	xxx (xx.x%)	xxx (xx.x%)	xxx (xx.x%)
Discontinued Trt ²	xxx (xx.x%)	xxx (xx.x%)	xxx (xx.x%)	xxx (xx.x%)	xxx (xx.x%)	xxx (xx.x%)	xxx (xx.x%)
Reasons for Discontinuation of Vacc. ²							
Death	xxx (xx.x%)	xxx (xx.x%)	xxx (xx.x%)	xxx (xx.x%)	xxx (xx.x%)	xxx (xx.x%)	xxx (xx.x%)
Adverse Experience	xxx (xx.x%)	xxx (xx.x%)	xxx (xx.x%)	xxx (xx.x%)	xxx (xx.x%)	xxx (xx.x%)	xxx (xx.x%)
Reactogenicity Symptom	xxx (xx.x%)	xxx (xx.x%)	xxx (xx.x%)	xxx (xx.x%)	xxx (xx.x%)	xxx (xx.x%)	xxx (xx.x%)
Other Clinical Event	xxx (xx.x%)	xxx (xx.x%)	xxx (xx.x%)	xxx (xx.x%)	xxx (xx.x%)	xxx (xx.x%)	xxx (xx.x%)
Unable to Contact / Out of Window	xxx (xx.x%)	xxx (xx.x%)	xxx (xx.x%)	xxx (xx.x%)	xxx (xx.x%)	xxx (xx.x%)	xxx (xx.x%)
Participant Refused Vaccination	xxx (xx.x%)	xxx (xx.x%)	xxx (xx.x%)	xxx (xx.x%)	xxx (xx.x%)	xxx (xx.x%)	xxx (xx.x%)
Other	xxx (xx.x%)	xxx (xx.x%)	xxx (xx.x%)	xxx (xx.x%)	xxx (xx.x%)	xxx (xx.x%)	xxx (xx.x%)
Missing	xxx (xx.x%)	xxx (xx.x%)	xxx (xx.x%)	xxx (xx.x%)	xxx (xx.x%)	xxx (xx.x%)	xxx (xx.x%)

¹Also include participants who discontinued vaccinations due to HIV infection, in order to obscure their numbers.

²Excludes discontinuations due to HIV infection.

HVTN 702: A phase 2b/3 trial of ALVAC/gp120+MF59 vs. Placebo in South Africa
Open Report for DSMB meeting on [Date]. Data cutoff date: [Date].

Table RETEN1. Visit Retention – Overall and by Study Site

	Total	Soweto - Bara	Soshanguve	Durban - Verulam	Cape Town - Emavundleni	Tembisa	Cape Town - Khayelitsha
Participants Enrolled	xxx	xxx	xxx	xxx	xxx	xxx	xxx
Month 1 / Vaccination 2							
Expected for Visit	xxx	xxx	xxx	xxx	xxx	xxx	xxx
Retained	xxx (xx.x%)	xxx (xx.x%)	xxx (xx.x%)	xxx (xx.x%)	xxx (xx.x%)	xxx (xx.x%)	xxx (xx.x%)
Missed Visit	xxx (xx.x%)	xxx (xx.x%)	xxx (xx.x%)	xxx (xx.x%)	xxx (xx.x%)	xxx (xx.x%)	xxx (xx.x%)
Terminated	xxx (xx.x%)	xxx (xx.x%)	xxx (xx.x%)	xxx (xx.x%)	xxx (xx.x%)	xxx (xx.x%)	xxx (xx.x%)
Permanently Discontinued Vaccination	xxx (xx.x%)	xxx (xx.x%)	xxx (xx.x%)	xxx (xx.x%)	xxx (xx.x%)	xxx (xx.x%)	xxx (xx.x%)
